6.6 Dose Modification

SAD and single dose expansion

Not Applicable.

MAD

On Day 15 or Day 29, treatment can be skipped at the Investigator's discretion based on safety reasons that interrupt IP administration (e.g., ear canal skin irritation, mild otorrhea). Subjects should be encouraged to return to the office for evaluation and additional IP administration within the Day 15 or Day 29 visit windows. In the case that the investigator is unable to conduct IP administration for anything other than safety reasons, consultation with the sponsor may be required.

Multiple dose expansion

The statement above for MAD is also applicable to the multiple dose expansion. Additionally, the treatment on Day 15 or Day 29, treatment will be skipped in cases where complete closure is confirmed. If the perforation is detected on Day 29 after treatment was skipped on Day 15, IP administration can be conducted.

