5.4 Exploratory Endpoints

Single dose phase:

- Complete closure of TMP for post baseline visits at Day 2, Day 3 (evaluations at this visit will only be performed for cohorts 1, 2 and 3), Week 1, Week 2 and Week 4 for SAD and Week 2, Week 4 and Week 8 for single dose expansion
For the observed response definition, refer to Section [5.3](#).
- Change from baseline in the ratio of TMP size per total area of tympanic membrane for post baseline visits at Day 2, Day 3 (evaluations at this visit will only be performed for cohorts 1, 2 and 3), Week 1, Week 2 and Week 4 for SAD and Week 2, Week 4 and Week 8 for single dose expansion
- Change from baseline in TMP size for post baseline visits at Day 2, Day 3 (evaluations at this visit will only be performed for cohorts 1, 2 and 3), Week 1, Week 2 and Week 4 for SAD and Week 2, Week 4 and Week 8 for single dose expansion

Multiple dose phase:

- Complete closure of TMP for post baseline visits at Week 1, Week 2, Week 3, Week 4, Week 5 and Week 8 for MAD and Week 2, Week 4, Week 6, Week 8 and Week 12 for multiple dose expansion

For the observed response definition, refer to Section [5.3](#).

- Change from baseline in the ratio of TMP size per total area of tympanic membrane for post baseline visits at Week 1, Week 2, Week 3, Week 4, Week 5 and Week 8 for MAD and Week 2, Week 4, Week 6, Week 8 and Week 12 for multiple dose expansion

- Change from baseline in TMP size for post baseline visits at Week 1, Week 2, Week 3, Week 4, Week 5 and Week 8 for MAD and Week 2, Week 4, Week 6, Week 8 and Week 12 for multiple dose expansion

Single and multiple dose phases:

- Time to closure of TMP

Time to closure of TMP (days):

TMP closure date - first dose date + 1. If the TMP is not closed, then time to closure will be set to missing.

- Size of TMP $\leq 5\%$ of pars tensa surface area after treatment

Observed response:

Using the non-missing size of TMP per pars tensa surface area, an observed response is

Yes: if the post baseline size of the TMP per pars tensa surface area $\leq 5\%$ and the size of the TMP per pars tensa surface area is smaller than baseline,

No: if the above condition is false.

Ratio of TMP size per total area of tympanic membrane will be used in the above calculation as an approximation for TMP per pars tensa surface area.

- Size of TMP $\leq 1\%$ of pars tensa surface area (pin point perforation) after treatment

Observed response:

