6 STATISTICAL METHODOLOGY

6.1 General Considerations

Continuous data will be summarized descriptively including the number of subjects (n), mean, standard deviation (SD) and/or standard error, median, minimum and maximum.

Categorical data will be summarized by frequencies and percentages. Percentages by categories will be based on the number of subjects with no missing data, i.e. the percentages for the non-missing categories will add up to 100%.

For SAD and MAD, results will be presented by ASP0598 treatment group in each cohort and placebo group where placebo subjects will be pooled across cohorts.

For single dose expansion and multiple dose expansion, results will be presented by each ASP0598 treatment group and placebo group.

All statistical comparisons between ASP0598 and placebo will be conducted using 2-sided tests at $\alpha = 0.05$ significance level, unless stated otherwise. For dose expansion phase, a hierarchical testing method will be used to control familywise error rate where the highest dose group vs placebo will be tested first. Refer to Section [6.4.2](#) for details.

All data summarization and analyses will be performed using SAS® Version 9.4 or higher on Redhat Enterprise Linux. Specifications for tables, listings, and figures (TLF) formats can be found in the TLF specifications.

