6.4 Analysis of Efficacy

Efficacy analyses will be presented by treatment group for FAS, unless specified otherwise.

For the endpoint complete closure of TMP at Week 12/Week 16 in dose expansion, based on the interim analysis results, if 3 treatment groups are selected, hierarchical testing method will be used to control familywise error rate where the highest dose group vs placebo will be tested first. Refer to Section [6.4.2](#) for details. If 2 treatment groups are selected, no multiplicity adjustment is needed.

For continuous endpoints, descriptive statistics will be used to summarize baseline value, post baseline value and change from baseline at each specified post baseline analysis visit by treatment group.

For categorical endpoints, number and percentage of subjects will be used to summarize baseline value and post baseline value at each specified post baseline analysis visit by treatment group. Difference from placebo will be presented, where applicable.

[Table 1](#) and [Table 2](#) provides list of variables that will be summarized for categorical endpoints using number and percentage of subjects and for continuous endpoints using descriptive statistics respectively.

[Table 3](#) provides an overview of efficacy analyses of secondary and exploratory variables for dose expansion phase.

Table 1 Categorical Efficacy Variables for Number and Percentage of Subjects

Variable	Analysis Visits
Observed response for complete closure of TMP as assessed by site investigator	SAD: Baseline, Day 2, Day 3*, Week 1, Week 2, Week 4, Week 8 and End of Study (EOS) Single dose expansion: Baseline, Week 2, Week 4, Week 8, Week 12 and EOS MAD: Baseline, Week 1, Week 2, Week 3, Week 4, Week 5, Week 8, Week 12 and EOS Multiple dose expansion: Baseline, Week 2, Week 4, Week 6, Week 8, Week 12, Week 16 and EOS

Table continued on next page

Variable	Analysis Visits
Observed response for complete closure of TMP as assessed by central reader	
SAD: Baseline, Day 2, Day 3*, Week 1, Week 2, Week 4, Week 8 and End of Study (EOS)
 
Single dose expansion: Baseline, Week 2, Week 4, Week 8, Week 12 and EOS
 
MAD: Baseline, Week 1, Week 2, Week 3, Week 4, Week 5, Week 8, Week 12 and EOS
 
Multiple dose expansion: Baseline, Week 2, Week 4, Week 6, Week 8, Week 12, Week 16 and EOS

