Imputed response for complete closure of TMP as assessed by site investigator	
SAD: Week 8
 
Single dose expansion: Week 12 primary analysis and Week 12 sensitivity analysis
 
MAD: Week 12
 
Multiple dose expansion: Week 12 and Week 16 primary analysis and Week 16 sensitivity analysis

Imputed response for complete closure of TMP as assessed by central reader	
SAD: Week 8
 
Single dose expansion: Week 12 primary analysis and Week 12 sensitivity analysis
 
MAD: Week 12
 
Multiple dose expansion: Week 12 and Week 16 primary analysis and Week 16 sensitivity analysis

Reduction from baseline in size of TMP to less than or equal to 5% of pars tensa surface area 
 ● Observed response ● Observed response where subjects with $\leq 5\%$ at baseline are excluded 	
SAD: Week 8 and EOS
 
Single dose expansion: Week 8, Week 12 and EOS
 
MAD: Week 12 and EOS
 
Multiple dose expansion: Week 12, Week 16 and EOS

Reduction from baseline in size of TMP to less than or equal to 1% of pars tensa surface area 
 ● Observed response ● Observed response where subjects with $\leq 1\%$ at baseline are excluded 	
Observed response for percentage improvement from baseline in A-B gap by PTA $\geq 50\%$ (improvement of conductive hearing)	
Observed response for improvement from baseline in air conduction hearing by PTA $\geq 15\text{ dB}$	
SAD: Week 8 and EOS
 
Single dose expansion and MAD: Week 12 and EOS

Observed response for A-B gap after treatment was 15 dB or less	
Multiple dose expansion: Week 16 and EOS

Observed response for air conduction hearing threshold after treatment was 30 dB or less	
Type of tympanogram	
SAD: Baseline, Week 8 and EOS
 
Single dose expansion and MAD: Baseline, Week 12 and EOS
 
Multiple dose expansion: Baseline, Week 12, Week 16 and EOS

*Day 3 evaluations will only be performed for cohorts 1, 2 and 3

Table 2 Continuous Efficacy Variables for Descriptive Statistics

Variable	Plots	Analysis Visits
Ratio of TMP size per total area of tympanic membrane	SAD and MAD: Mean +/- SE for the change from baseline vs Analysis Visit by treatment group (overlay)	SAD: Baseline, Day 2, Day 3 ^b , Week 1, Week 2, Week 4, Week 8 and EOS

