TMP size	Dose expansion: Least squares mean +/- SE for the change from baseline vs Analysis Visit by treatment group (overlay) ^a	Single dose expansion: Baseline, Week 2, Week 4, Week 8, Week 12 and EOS MAD: Baseline, Week 1, Week 2, Week 3, Week 4, Week 5, Week 8, Week 12 and EOS Multiple dose expansion: Baseline, Week 2, Week 4, Week 6, Week 8, Week 12, Week 16 and EOS EOS visit will not be included in the plot.
Time to closure of TMP ^c	Not Applicable	Not Applicable
Air conduction hearing at 250 Hz, 500 Hz, 1 kHz, 2 kHz, 4 kHz and 8 kHz		
Mean air conduction hearing	SAD, MAD and Dose expansion: Individual subject plot of air conduction hearing and bone conduction hearing for each frequency and mean by Analysis Visit (Overlay)	SAD: Baseline, Week 8 and EOS Single dose expansion and MAD: Baseline, Week 12 and EOS Multiple dose expansion: Baseline, Week 12, Week 16 and EOS
Bone conduction hearing at 500 Hz, 1 kHz, 2 kHz and 4 kHz		
Mean bone conduction hearing		
A-B gap at 500 Hz, 1 kHz, 2 kHz, and 4 kHz		
Mean A-B gap		
ECV by tympanometry	Not Applicable	

^a from the MMRM model as described in Section 6.4.2 and Section 6.4.3.

^b Day 3 evaluations will only be performed for cohorts 1, 2, and 3

^c change from baseline is not applicable.

For the secondary endpoint complete closure of TMP at Week 12 (single dose expansion) and Week 16 (multiple dose expansion), number and percentage of subjects will be provided by treatment group for the following subgroups:

- Sex,
- Race,
- Age group,
- BMI group,
- CTMP duration group (≤ 1 year, > 1 to ≤ 10 years, > 10 years),
- Tobacco history (Yes, No),
- Causation of TMP,
- Diabetes history
- Stratification factor TMP size group,
- Baseline TMP size group per total area of tympanic membrane from central imaging.

For the dose expansion secondary endpoints (change from baseline in ratio of TMP size per total area of tympanic membrane and change from baseline in TMP size), descriptive statistics will be used to summarize the Week 12 (single dose expansion) and Week 16 (multiple dose expansion) analysis visit results by treatment group for the subgroup baseline TMP size group per total area of tympanic membrane from central imaging.

For the categories of the subgroup variables, refer to Section [6.2.3](#).

Table 3 Overview of Efficacy Analysis for Dose Expansion

Endpoint Type	Analysis Variable	Analysis Method

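### Time to closure is set to missing for ears that do not close, so the by-arm summaries describe closers only and can understate, hide or reverse the timing difference

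*SAP*

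**What the plan says.** SAP 5.4 derives time to closure in days as "TMP closure date - first dose date + 1" and adds: "If the TMP is not closed, then time to closure will be set to missing". In SAP 6.4 the variable appears in Table 2, headed "Continuous Efficacy Variables for Descriptive Statistics", in the row "Time to closure of TMP". Plots and analysis visits are marked not applicable for that row, and a footnote says that "change from baseline is not applicable", so the value itself is summarised by treatment group. SAP 6.1 sets the format: "Continuous data will be summarized descriptively including the number of subjects (n), mean", and so on.

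Protocol 9.4.3 also lists time to closure among the continuous exploratory endpoints and plans no statistical analysis of it. Neither document gives a censoring rule, Kaplan-Meier estimate, cumulative incidence or restricted mean for this endpoint.

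Two related provisions matter. SAP Table 1 reports closure by visit for two assessors, the site investigator and the central reader ("Observed response for complete closure of TMP as assessed by central reader"). Protocol 6.6 foresees, for the multiple dose expansion, that a closed ear may reopen: "If the perforation is detected on Day 29 after treatment was skipped on Day 15, IP administration can be conducted".

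**The concern.** For an ear still open at its last assessment we know that closure takes longer than the observed follow-up. That is right-censoring. Setting the value to missing discards the information and restricts each column to subjects who closed. Closure is the outcome the drug is meant to change, so the two columns describe differently selected subsets and randomisation no longer protects the comparison between them.

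A drug that closes difficult ears late adds long times to its own column. The corresponding placebo ears stay open and vanish from theirs. Such a drug could look slower than placebo because it works.

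The derivation also leaves two choices open: which assessor's date is the closure date, and whether first closure counts if the ear later reopens. Different programmers could derive different values from the same data.

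**Working it through.** **Inputs from the documents.** Closure rates of 10% (placebo) and 80% (higher-concentration group), and 13 subjects per group: SAP 3 and Protocol 9.1. Expansion visits: Days 15, 29, 57, 85 (single dose) and Days 15, 29, 43, 57, 85, 113 (multiple dose): Protocol 4.1. The plan states no figure for time to closure.

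**The plan's sample size reproduces.** Exact Fisher power for 10% vs 80% at two-sided 0.05 is 90.5% with 11 per group, and 11/0.9 = 12.2 rounds up to 13.

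**How many subjects enter the summary.**
- Expected closers: 13 × 0.1 = 1.3 placebo; 13 × 0.8 = 10.4 active. By rule, 90% of placebo and 20% of active values are expected to be missing.
- P(no placebo closer) = 0.9^13 = 25.4%.
- P(at most one) = 0.9^13 + 13 × 0.1 × 0.9^12 = 62.1%.
- Dose escalation, with 4 pooled placebo subjects in each of SAD and MAD, if the 10% rate is applied there: 0.4 expected closers; P(none) = 0.9^4 = 65.6%.

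**What the summary would show.** The documents give no closure timing, so the patterns below are assumptions. For an arm with closure probability p and last visit on day T:
- closers-only mean = Σ(day × probability of closing at that visit) / p
- all-subjects mean = Σ(day × probability of closing at that visit) + (1 − p) × T, which holds open ears at the last visit

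Under constant hazard, λ = −ln(1 − p)/T, with closure first seen at the next scheduled visit.

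| Assumed pattern | Closers only, active vs placebo (days) | All subjects kept, active vs placebo (days) |
|---|---|---|
| (a) Constant hazard, single dose | 42.8 vs 53.4, gap 10.7 | 51.2 vs 81.8, gap 30.6 |
| (b) Constant hazard, multiple dose | 51.7 vs 66.0, gap 14.3 | 63.9 vs 108.3, gap 44.4 |
| (c) Closers spread evenly over the four single dose visits in both arms | 46.5 vs 46.5, no gap | 54.2 vs 81.2 |
| (d) Drug adds mainly later closures, single dose | 52.6 vs 22, reversed | 59.1 vs 78.7 |

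Pattern (c): (15 + 29 + 57 + 85)/4 = 46.5. Active kept: 0.8 × 46.5 + 0.2 × 85 = 54.2. Placebo kept: 0.1 × 46.5 + 0.9 × 85 = 81.15.

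Pattern (d): both arms have 5% closing at Day 15 and 5% at Day 29. Active has a further 70% split equally over Days 29, 57 and 85, with mean day 57.
- Active sum: 0.05 × 15 + 0.05 × 29 + 0.7 × 57 = 42.1. Closers only: 42.1/0.8 = 52.6. Kept: 42.1 + 0.2 × 85 = 59.1.
- Placebo sum: 0.05 × 15 + 0.05 × 29 = 2.2. Closers only: 2.2/0.1 = 22. Kept: 2.2 + 0.9 × 85 = 78.7.

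**Sampling noise.** In 200,000 simulated trials with 13 per arm, about 74.5% have a closer in both arms. Among those, under constant hazard, the active closers-only mean is the longer one in about 32% (single dose) and 34% (multiple dose), although the drug is faster.

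**The case against.** The endpoint is exploratory, no test is planned, and n is shown, so a placebo column resting on none or one subject would be visible. Table 1 gives closure by arm at every visit, and with fixed visits and little dropout a Kaplan-Meier curve would largely restate it. A mean among closers is a legitimate conditional description if labelled as such. These points limit the impact and stand to that extent. But nothing in the protocol or SAP labels the row as closers only, and the other tables warn the reader without correcting it.

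The all-subjects means used as the benchmark are not what the proposed fix reports, and the placebo median will almost certainly not be reached. That is correct. The means show the direction and possible size of the distortion; they are not proposed as an output.

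The timing patterns are chosen. Reversal in expectation needs something like pattern (d). Under constant hazard the expected order is right, and the 32% and 34% become roughly 24% and 25% of all trials once those without a closer in both arms are counted. So understating, hiding or reversing is a possibility, not a certainty.

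On the assessor, Protocol 7.1.1 gives evaluation of complete closure to the central imaging vendor, and SAP 6.9.2.1 takes it from imaging. The documents therefore point to the central reader, and this part of the concern needs only an explicit statement. The reopening provision applies to the multiple dose expansion only.

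**Conclusion.** The concern holds. The rule as written conditions the summary on closure and should be changed. At the plan's 10% and 80% with 13 per group, the comparison would rest on about 1.3 placebo and 10.4 active subjects, with a one-in-four chance of no placebo value at all. These counts apply to the higher-concentration group; the plan assumes no rate for a low-dose group.

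How far the means mislead depends on closure timing, which the documents do not give. Across the assumed patterns the result ranges from a gap about one third of the all-subjects gap (10.7 against 30.6 days; 14.3 against 44.4) to no gap or a reversed order. The primary safety endpoints and the tested secondary closure comparison are unaffected.

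**What to change.** Replace the rule in SAP 5.4 and the Table 2 row with wording to this effect:

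- The event is first complete closure by the central reader, dated by the image; the investigator assessment is supportive.
- Subjects without closure are censored at their last perforation assessment.
- For the dose expansions, show by treatment group the Kaplan-Meier cumulative closure by scheduled visit, the median or a statement that it was not reached, number closed over number in group, and number later reopened.
- For SAD and MAD, list individual times with number closed over number in group.
- Drop the closers-only mean. Add no hypothesis test.

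Closure is seen only at visits, so the times are visit-dated; a footnote should say so.

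The cost is SAP wording and one changed table or figure, from data already collected. SAP 1 requires changes to the dose escalation part to be approved before that part is unblinded for its interim analysis, so the SAD and MAD listing must respect that timing. The placebo curve will still rest on about one event. Its median needs 7 closures among 13, which has probability of about 0.01% at a 10% rate. Reporting few closures and a median not reached is nevertheless accurate, whereas a mean from one ear is not.
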